18.0 Confidentiality

A. Confidentiality of Study Data

Describe the local procedures for maintenance of confidentiality of study data and any records that will be reviewed for data collection.

18.1 A. Where and how will all data and records be stored? Include information about: password protection, encryption, physical controls, authorization of access, and separation of identifiers and data, as applicable. Include physical (e.g. paper) and electronic files.

Response:

Study 2:

Electronic informed consent documents will be stored on the secure Qualtrics servers. All electronic data files will not include identifying information. All participants will be given an alpha-numeric code that will identify their data. The file that links their identity with this code will be password protected and kept on a separate server from all password protected data files.

A. How long will the data be stored?

Response:

The identifying data will be stored for five years after the study has been completed.

18.2 A. Who will have access to the data?

Response:

The PI, Co-Is, and Research Staff (Project manager and Research Technicians), and Computer personnel as needed.

18.3 A. Who is responsible for receipt or transmission of the data?

Response:

PI [name] or project coordinator. Appropriate Computer Department personnel, who will only have access to de-identified data.

18.4 A. How will the data be transported?

Response:

Study 2: All data collected through the tablets for questionnaires, online education programs, and online follow-up surveys will be encrypted and transmitted to data files stored on UB Box.

Confidentiality of Study Specimens

Describe the local procedures for maintenance of confidentiality of study specimens.

N/A: No specimens will be collected or analyzed in this research.
(*Skip to Section 19.0*)

18.5 B. Where and how will all specimens be stored? Include information about: physical controls, authorization of access, and labeling of specimens, as applicable.

Response:

18.6 B. How long will the specimens be stored?

Response:

18.7 B. Who will have access to the specimens?

Response:

18.8 B. Who is responsible for receipt or transmission of the specimens?

Response:

18.9 *B. How will the specimens be transported?*

Response:

19.0 Provisions to Monitor the Data to Ensure the Safety of Subjects

- N/A:** This study is not enrolling subjects, or is limited to records review procedures only. This section does not apply.

NOTE: *Minimal risk studies may be required to monitor subject safety if the research procedures include procedures that present unique risks to subjects that require monitoring. Some examples include: exercising to exertion, or instruments that elicit suicidality or substance abuse behavior. In such cases, N/A is not an acceptable response.*

19.1 *Describe the plan to periodically evaluate the data collected regarding both harms and benefits to determine whether subjects remain safe.*

Response:

Study 2:

PI [name] will closely monitor all aspects of the research and will be informed of any adverse or potentially adverse events that occur in the course of the intervention groups and research contact with participants. All serious adverse events during the intervention and follow-up period will be reported (in writing) to the University at Buffalo Institutional Review Board, and the NIH Program Official within 48 hours, and the Chair of the Psychology Department at the University of Buffalo also will be notified of all adverse events.

The three potential risks to participants include breach of confidentiality, distress or discomfort with the intervention material, and indication of intent to harm oneself or another. Several steps will be taken to ensure the confidentiality of the data. All electronic informed consent acknowledgement will be kept in a computer file separate from all survey data stored on the Qualtrics secure servers or the project UB Box. The audiotaped data files will be used for reliability checks for treatment fidelity purposes only and will be destroyed at the end of the study. PI [name] will closely monitor all research intervention sessions. All data collected through laptop computers also will be stored on UB box only accessible to authorized project staff. For the purpose of scientific publication, only group means will be reported, and individual participants will not be identified. To ensure participant anonymity, a separate list with the participants' names and contact information will be stored in a different location than their data (Secure data file on UB Box), and only

the research staff will have access. The second potential risk, participant discomfort as a result of intervention material or questionnaire assessments will be monitored carefully through feedback questionnaires, observations during in-person sessions, debriefing following in-person sessions, and through follow-up phone calls at the participant's request. Should a participant express discomfort during or following any of the intervention components, the source of this discomfort will be discussed in a clinically-sensitive manner. PI [name] will be notified and will place a call to the participant. In addition, all participants will be told that they can refuse to answer any questions they do not feel comfortable answering and can withdraw from the study at any time. The third risk involves having the participant report information to research staff that suggests she is a danger to herself or others. We discuss how this information will be handled below.

- a. Incidents during in-person intervention assessments. Should a participant become very agitated or report information that suggests she may be a danger to herself or others, the project staff will immediately inform PI [name], who has worked with this population of women for 20 years and has experience conducting suicidality/ homicidality assessments. In addition, Co-I [name] (Counseling Psychologist) will be available for consultation by phone if the PI is not available. If the PI or Co-I determines that the participant may pose an imminent threat, they will immediately call 911 or the Buffalo General Hospital Psychiatric Emergency Room to obtain a psychiatric evaluation. Should the psychiatric evaluation result in an inpatient admission, the participant's study participation will be terminated. If a referral to the Psychiatric Emergency Room is not warranted, [name] and the other Co-I will discuss steps that should be taken to ensure the safety and well-being of the participant.
- b. Ensuring validity of the data. Validity of the data will be ensured in several ways. First, measures for use in the study were selected carefully with regard to their established psychometric properties with women who have experienced sexual victimization and trauma. Data files will be checked on a scheduled basis for any irregularities.
- c. Appointment of a data and safety monitoring board (DSMB). Although this is not a Stage III clinical trial and, as such, does not require a DSMB, we have chosen to convene one as an extra measure of oversight given the serious and sensitive nature of sexual revictimization (SRV) experiences among young women. The DSMB will be convened during the Spring of 2022 and will meet twice through the end of the project to discuss any adverse and serious adverse events, and strategies for ensuring the safety and well-being of the study participants. All members of the DSMB will receive reports of adverse and serious adverse events that occur on the project. The DSMB will meet as soon as feasible following a serious adverse event.

19.2 Describe what data are reviewed, including safety data, untoward events, and efficacy data.

Response:

Study 2:

Negative reactions of participants to the intervention material will be monitored and reported. Incidents of sexual victimization – frequency and severity will be carefully monitored and used to assess the efficacy of the intervention as will changes in drinking patterns.

Describe any safety endpoints.

Response:

Study 2: Outcomes at the follow-up points of 3 and 6 months will be monitored carefully to determine what affect the intervention appears to be having on hazardous drinking and risks for sexual victimization.

19.3 Describe how the safety information will be collected (e.g., with case report forms, at study visits, by telephone calls with participants).

Response:

Study 2: At all group sessions, through all contact with participants during screening, e-mails, follow-up calls and data monitoring.

19.4 Describe the frequency of safety data collection.

Response:

Study 2: Safety data will be collected throughout the study.

19.5 Describe who will review the safety data.

Response:

The PI, [name] will review the safety data.

19.6 Describe the frequency or periodicity of review of cumulative safety data.

Response:

Study 2: Data will be reviewed for the randomized controlled trial (RCT) on an ongoing basis to determine whether the anticipated changes in the outcomes (reduced hazardous drinking and low or no occurrence of sexual victimization) are observed.

19.7 Describe the statistical tests for analyzing the safety data to determine whether harm is occurring.

Response:

Study 2: No specific tests given the small number of participants. A preponderance of negative events seen through descriptive analyses of follow up data – for example, high rates of sexual victimization at 3-month and 6-month follow-up or increased hazardous drinking at follow-ups.

19.8 Describe any conditions that trigger an immediate suspension of the research.

Response:

Study 2: Multiple serious adverse events.

20.0 Withdrawal of Subjects

N/A: This study is not enrolling subjects. This section does not apply.

20.1 Describe anticipated circumstances under which subjects may be withdrawn from the research without their consent.

Response:

Study 2: If participants are being noncompliant with the intervention, report homicidal thoughts or feelings, or report suicidal thoughts or feelings or if information comes to light during the study period that the participant was not actually eligible for the study.

20.2 Describe any procedures for orderly termination.

NOTE: Examples may include return of study drug, exit interview with clinician. Include whether additional follow up is recommended for safety reasons for physical or emotional health.

Response:

Study 2: An exit interview with [name] will be conducted and if the participant is found to be a danger to herself or others appropriate measures will be taken to insure her safety (i.e., calling 911, obtaining a psychiatric evaluation).

20.3 Describe procedures that will be followed when subjects withdraw from the research, including retention of already collected data, and partial withdrawal from procedures with continued data collection, as applicable.

Response:

Study 2: We will retain data that has already been collected but no further data will be collected. Participants will not be withdrawn from the study once they are enrolled and randomized to the study. Their data will be retained for analyses under the intent to treat principle.

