10.0 Procedures Involved

*10.1 Provide a description of **all research procedures or activities** being performed and when they are performed once a subject is screened and determined to be eligible. Provide as much detail as possible.*

NOTE: This should serve as a blueprint for your study and include enough detail so that another investigator could pick up your protocol and replicate the research. For studies that have multiple or complex visits or procedures, consider the addition of a schedule of events table in in your response.

Response:

Study 2:

During the Stage 1b Randomized Controlled Trial of the active intervention, the first group session will focus on viewing each of 4 cue recognition training videos and the Interventionist will lead a discussion intended to highlight the risk cues in each of the videos. After the session, links and passwords will be sent via email to each participant for the online safe dating and safe drinking learning modules and participants will be asked to complete them prior to the second group session, which will take place about one week after the first session. This second group session will elicit feedback on the dating and drinking learning modules (e.g., length, ease of use, engagement, interest). The training videos will be viewed again individually and participants will engage in behavioral skills rehearsal of appropriate responses in paired role plays with feedback from the PI and Interventionist. During the behavioral rehearsal segment, the PI or Interventionist will engage the group in a discussion of emotional barriers to engaging in appropriate dating and drinking safety behaviors (e.g., "I feel bad for the guy", "He might get really mad, "I might miss out on being with a great guy") and strategies for overcoming these barriers. Adaptive emotion regulation strategies will include cognitive reappraisal, distress tolerance, mindfulness of current emotions, acceptance, and problem solving. Immediately following this session, the post-intervention measures, including feedback on the intervention content and process, will be completed. Following the in-person RPCW sessions, a debriefing will occur to ensure that women have an opportunity to discuss any emotional discomfort or distress with the interventionist. Women will receive \$30 for completion of the post-intervention measures.

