At the beginning of the first in-person session and at the end of the second in-person session, for both the RPCW active intervention and the HEC condition, three standardized instruments will be administered to participants. **Participants will be seated a minimum of 6 feet apart in the group session room and administered these instruments on an individual laptop with earphones to allow them privacy.** These include the Video Vignette Risk Perception Measure (VVRPM) which assesses women's standardized ability to assess sexual assault risk cues. The Adult Faces test from the Diagnostic Analysis of Nonverbal Accuracy 2 (DANVA2) which is used to measure an individual's general ability to sensitivity to perceive nonverbal cues, and the sDERS a measure used to assess state emotion regulation (assessed using a web-based platform as are the other survey measures for the study). All data will be uploaded off of these laptops and saved to the project UB Box at the end of each in-person session.

Outlines for the in-person RPCW and HEC sessions are attached and links to the on-line learning units for both the RPCW and HEC are included for review.

10.2 Describe what data will be collected.

NOTE: For studies with multiple data collection points or long-term follow up, consider the addition of a schedule or table in your response.

Response:

Study 2:

Participants will participate in the intervention over about one week. They will attend two in-person group intervention sessions about one week apart, and complete two on-line units during the intervening week. They will be asked to complete follow-up on-line assessment surveys at 3 months and 6 months post intervention.

The follow-up surveys will be administered online and are included for review.

 *10.3 List any instruments or measurement tools used to collect data (e.g. questionnaire, interview guide, validated instrument, data collection form).*

Include copies of these documents with your submission.

Response:

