17.0 Data Management and Analysis

17.1 Describe the data analysis plan, including any statistical procedures. This section applies to both quantitative and qualitative analysis.

Study 2:

Data Analyses

For the RCT, data will be analyzed according to the intention-to-treat principle [122]. All participants who complete the baseline assessment will be followed (i.e., post-intervention, 3-month and 6-month post-intervention) regardless of treatment participation. Given our experience and past record of retaining participants in longitudinal studies and the relatively brief period of follow-up (6-mos), dropout due to attrition is expected to be low. We anticipate no more than 5% of data will be missing through attrition or wave nonresponse (i.e., not completing all measures at a given time period). To adjust for any missing assessments, we will use multiple imputation procedures [123, 124].

We have three specific hypotheses for the RCT, our analyses are organized below for each hypothesis.

Hypothesis a: Participants in the RPCW intervention will report fewer days of hazardous drinking and improved perception of SRV risk cues on the video risk perception measure (primary outcomes) as compared with participants in the HEC condition.

Differences in relevant outcome variables (e.g., number of heavy drinking days, perception of SRV risk cues) will be tested using a 2 (Condition: RPCW vs. HEC) x 4 (Time: baseline, post-treatment, and 3- and 6-month post-treatment) repeated-measures analysis of variance (RM-ANOVA). The primary effects of interest are the intervention condition main effect and the intervention x time interaction. If a significant condition by time interaction is found, it means that (a) change over time in heavy drinking days differs across intervention conditions and (b) the effect of intervention condition on the outcome is different across time. Therefore, a significant intervention condition by time interaction will be explored by computing the conditional effect of time for each intervention condition and (b) the conditional effect of treatment condition at each of the four time points.

Hypothesis b: Participants in the RPCW intervention will report increased knowledge of safe dating practices and protective behavioral (drinking) strategies (secondary outcomes) compared with participants in the HEC condition.

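### Protocol 20.1 lets staff withdraw women from the research for noncompliance, against 20.3 and the follow-up rule in 17.1 and the SAP

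*Protocol*

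**What the plan says.** Protocol section 20.1 responds to a prompt about when "subjects may be withdrawn from the research without their consent". The first circumstance it gives is "If participants are being noncompliant with the intervention". The others are homicidal or suicidal thoughts and ineligibility discovered later.

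Section 20.3 describes what happens on withdrawal: "We will retain data that has already been collected but no further data will be collected". It then says "Participants will not be withdrawn from the study once they are enrolled and randomized to the study", lists no exception, and adds "Their data will be retained for analyses under the intent to treat principle".

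Section 17.1 of the protocol states the follow-up rule, and the SAP repeats it word for word under Data Analyses: "All participants who complete the baseline assessment will be followed (i.e., post-intervention, 3-month and 6-month post-intervention) regardless of treatment participation". Both expect at most 5% missing data, from attrition or wave nonresponse, and plan multiple imputation.

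**The concern.** Section 20.1 concerns removal from the research, not only from the sessions. A woman cannot be noncompliant with RPCW or HEC before she is assigned to one of them, so this ground falls on the women whom 20.3 protects from withdrawal. It is also discretionary, and noncompliance is not defined, so its use is left to staff after assignment.

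If the ground were used and data collection stopped, missing outcomes would depend on adherence after randomisation, and the loss could differ by arm. The outcomes affected are hazardous drinking (a primary outcome) and SRV (exploratory) at 3 and 6 months. Section 19 relies on the same follow-up data as safety endpoints and for the descriptive judgement of harm. The effect sizes are meant to prepare a Stage II trial, so a distortion here would carry forward. Keeping earlier data under intention to treat does not supply outcomes that were never collected.

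**Working it through.** **1. The rules side by side.** Take a randomised woman who completes baseline and then skips the modules or session 2.

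| Place | What happens to her |
|---|---|
| Protocol 20.1 | May be removed from the research without consent |
| Protocol 20.3, on randomised women | Is not withdrawn |
| Protocol 17.1 and SAP | Is followed at post-intervention, 3 and 6 months |
| Protocol 20.3, on procedures after withdrawal | If withdrawn, nothing more is collected |

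The second and third rows agree. The first conflicts with both. The fourth turns use of the first into missing outcomes, if it is read to cover withdrawal by the investigator. The prompt for that sentence is about subjects who withdraw, so it may be meant for voluntary withdrawal only, but the text does not say so.

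**2. Possible bias (illustration).** From the documents: 48 women per arm, four assessments, and correlations r = .3 to .9 between assessments (17.2). Assumed, because the documents give no figures: a fraction p = 0.10 to 0.20 of one arm lost (4.8 to 9.6 of 48 women), none lost in the other arm, lost women differing from retained women in that arm by D = 0.3 to 0.8 SD at follow-up, and equal SDs across waves.

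- Before imputation, the shift is p × D: 0.10 × 0.3 = 0.03 SD to 0.20 × 0.8 = 0.16 SD.
- After regression-based imputation from baseline, with baseline difference D0, the shift is p × (D − r × D0).
- If D0 = D, this is p × D × (1 − r). At p × D = 0.03 it is 0.003 (r = .9) to 0.021 (r = .3). At p × D = 0.16 it is 0.016 (r = .9) to 0.112 (r = .3).
- If D0 = 0, imputation from baseline removes nothing and 0.03 to 0.16 SD remains.

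**3. Does the 5% expectation rule this out?** Planned assessments: 96 × 4 = 384. Losing two waves gives 4.8 × 2 / 384 = 2.5% to 9.6 × 2 / 384 = 5.0%. So the 5% figure does not exclude the scenario, although the upper end uses the whole allowance.

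**4. Precision for Hypothesis c.** The stated w = .29 reproduces: with 96 women, 1 df and alpha .05, a noncentral chi-square with noncentrality 96 × .29² = 8.07 gives 81.1% power. If only women with observed outcomes were analysed and 4, 10 or 20 were lost across both arms (92, 86 or 76 left), power at w = .29 would be 79.4%, 76.7% or 71.5%. These losses are again assumed.

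**The case against.** The intended rule is arguably already clear: 20.3, 17.1 and the SAP all point to continued follow-up, and the outlier is one permissive phrase answering a form prompt. The analysis plan itself contains no error on this point. Since the SAP copies 17.1, there are two independent statements against 20.1, not three. This is fair, but it shows which text to change rather than removing the conflict.

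Outcomes are lost only if staff use the ground and also apply the stop on data collection. That stands: the loss could happen; it is not certain.

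Section 17.1 covers baseline completers. The laptop baseline measures are taken at the start of session 1 and the baseline survey is paid there, so a woman who never attends may fall outside it. This also stands, and it narrows the conflict with 17.1 to women who start and then stop. The conflict with 20.3 is unaffected.

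The magnitudes are assumed, and loss in one arm only is the extreme case. Women unable to commit to both sessions are excluded (6.2), the intervention lasts about a week, and HEC is a time and attention control with the same number of sessions and modules. A woman who skips modules but attends session 2 also has post-intervention data to impute from. Even 0.16 SD is below the standard error of a single-wave contrast, √(2/48) = 0.20 SD. All of this is correct and keeps the numbers illustrative. However, bias of this kind does not shrink with sample size, and it would enter the effect sizes carried to Stage II.

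The reach is limited. The video risk perception measure, the other primary outcome, is described only at sessions 1 and 2. A woman who misses session 2 lacks it whether or not she is withdrawn.

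**Conclusion.** The concern holds: section 20.1 is wrong as written. It permits, for noncompliance, a withdrawal from the research that 20.3 forbids and that defeats the follow-up rule in 17.1 and the SAP. That conclusion rests on the text alone and is held with high confidence.

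The numerical effect is unknown, because it depends on how often the ground is used and how noncompliant women differ. Under the assumptions above, up to 0.16 SD could remain after imputation. Similar loss in both arms would make it smaller, and the lower end is negligible. The point should be fixed because the inconsistency is certain and correcting it costs almost nothing, not because a large bias has been shown.

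**What to change.** - **20.1:** remove noncompliance as a ground for ending data collection. State that women who miss sessions or modules are still sent the 3- and 6-month surveys unless they withdraw consent, and are analysed in their assigned arm.
- **20.3:** limit the stop on data collection to women who withdraw consent, if that is what is meant.
- **Post-intervention wave (optional):** these measures are completed at the end of session 2 (10.1: "Immediately following this session, the post-intervention measures"). Say whether that survey will be offered online to women who miss the session, and acknowledge that the session-2 laptop risk perception measure may stay missing for them.
- **Safety and late-ineligibility grounds:** those in 20.1, and the ending of participation after an inpatient admission in 19.1, must also be reconciled with 20.3 and 17.1. No rule is proposed for them here.

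The cost is one wording change in 20.1 and one in 20.3. Section 10.2 already provides for remote follow-up ("The follow-up surveys will be administered online and are included for review"), and section 25.1 already pays for both surveys, so the 3- and 6-month waves need no new procedure. An online post-intervention survey would be a small added arrangement.
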